6.3.9. Schedule of Events Table

The Schedule of Events is provided in Table 4.

Table 4 Time and Events Schedule

Parameter	Screening Visit ^a (-28 to Day 1)	Baseline Visit (Day 1)	Day 15 Visit (Day 15 ±3 day)	Day 29 Visit (Day 29 ±3 days)	Day 57 Visit (Day 57 ±5 days)	Day 85 Visit ^b (Day 85 ±5 days)
	Visit 1	Visit 2	Visit 3	Visit 4	Visit 5	Visit 6
Written informed consent/assent	X					
Medical history/ Review of systems	X	X ^a				
Demographics	X					
Height and weight measurement	X					
Urine pregnancy test (WOCBP only)	X	X ^a		X	X	X
Urine drug screen	X	X ^a				
Eligibility criteria review	X	X ^a				
IGA	X	X ^a	X	X	X	X
Body Surface Area (BSA) of AD	X	X ^a	X	X	X	X
Signs of AD score		X	X	X	X	X
EASI score		X	X	X	X	X
Pruritus Score (I-NRS)		X	X	X	X	X
Laboratory blood draw (CBC and chemistry)		X				X
Urine collection for urinalysis		X				X
Photographs and Signs of AD scoring of target lesion (selected sites)		X	X	X	X	X
Randomize subject		X				
Study drug administration in clinic		X	X	X	X	
Study drug administration at home		Day 1 pm to Day 84 pm; final application prior to Day 85 Visit				
Concomitant medications query	X	X ^a	X	X	X	X
Adverse experience query		X	X	X	X	X
Weigh and Dispense study drug		X		X	X	
Collect and Weigh study drug			X ^c	X	X	X
Dispense Diary		X		X	X	
Collect Diary and review compliance			X ^c	X	X	X

^a If subject meets eligibility criteria, Screening and Baseline Visit can occur on the same day. If Screening and Baseline Visit are not concurrent, review of eligibility, Review of Systems, UPT, UDS, BSA of AD, IGA, and concomitant medications query will be repeated at the Baseline Visit.

^b If subject discontinues treatment early, Day 85 evaluations will be performed when possible.

^c On Day 15, review compliance only.

6.4. Concomitant Medications, Treatment and Procedures

All concomitant medications taken during study participation will be recorded on the case report forms (eCRFs). For this protocol, a prescription medication is defined as a medication that can be prescribed only by a properly authorized/licensed clinician. Medications to be reported in the eCRF are concomitant prescription medications, OTC medications, and non-prescription medications. In addition, vitamins, supplements and other non-pharmaceuticals products that are taken orally are to be reported in the eCRF. Any use of marijuana containing products will be reported.

Subjects will use their normal soaps or body washes throughout the study. Changes in soaps and body washes during the study should not occur. Subjects will be instructed to wash their body prior to the Baseline, Day 15, Day 29, and Day 57 Visits. The body should not be washed within 5 minutes prior to, or within 1 hour after application of study drug. Subjects must agree to maintain their regular use of sunscreens and moisturizers throughout the entire course of the study. Detailed dosing instructions will be provided to the subject.

6.5. Prohibited Medication, Treatment, and Procedures

The following medications, treatments, and procedures are prohibited for all subjects during the study.

- Treatable AD lesions cannot be washed or shaven within 5 minutes prior to or for 1 hour after application of study medication.
- Participation in a clinical study of any investigational product or procedure.
- Use of high dose (> 10,000 IU) Vitamin D.
- Use of systemic corticosteroids (inhaled or intranasal corticosteroid \leq 1000 μ g daily dose is acceptable), oral antibiotics, or anti-inflammatory drugs (occasional NSAIDs to treat ailments are permitted)
- Use of any topical agent, other than study drug, to treat AD.
- Use of any oral medication for the treatment of AD.
- Use of any medication that, in the opinion of the investigator, may affect the evaluation of the study product or place the subject at undue risk.
- Use of topical or oral antibiotics. If a subject gets an infection during the study that requires topical or oral antibiotics, the subject can be treated and allowed to remain on the study. The antibiotic use will be noted as a deviation.
- Photodynamic therapy.
- Use of tanning beds.

Subjects may use bland emollients to manage dry skin areas around, but not overlapping, the treatable AD lesions. Sunscreens may be applied to the skin areas around, but not overlapping, the treatable AD lesions.

Subjects should limit exposure of the treatment area to sunlight during the study. Suitable clothing and other protective garments should be worn throughout the study.

Subjects must not shower or wash the study application area for 1 hour after application of study drug. Subjects should avoid swimming and heavy exercise for 1 hour after application of study drug.

Subjects will wash their hands directly after application of study drug.

6.6. Rescue Medication, Treatments and Procedures

Systemic medications for treatment of AD are prohibited (see Section 6.5). If a subject is unable to continue the study without additional treatment for the lesion areas, or if they require systemic treatment, the appropriate treatment should be administered. Exacerbation of AD will be recorded as an AE. The site will notify the study monitor immediately if this occurs. The subject's continuation on the study will be decided on a case-by-case basis.

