### **5. EFFICACY AND SAFETY ENDPOINTS**

#### **5.1 Efficacy Endpoints**

##### **5.1.1 Primary Efficacy Endpoints**

The primary efficacy endpoint for the study is:

- The proportion of subjects with Investigator Global Assessment (IGA) success defined as an IGA score of “Clear” (0) or “Almost Clear” (1) with at least a 2-grade improvement from Baseline at Day 85

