#### **6.4.2 Intent-to-Treat Population**

All subjects in the randomized population who receive at least one application of study drug and have at least one post-Baseline efficacy assessment will be included in the ITT population and analyzed according to the randomized treatment group. All efficacy analyses will be presented using the ITT population.

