### **6.4.5 Per-Protocol Population**

All subjects in the ITT population who complete the Day 85 visit without noteworthy study protocol violations will be included in the PP population and analyzed according to the treatment group received. The PP population will include subjects in the ITT population who do not meet any of the following criteria:

- Violated the inclusion/exclusion criteria;
- Have taken any interfering concomitant medication;
- Has missing IGA assessment at the Day 85 visit;
- Have missed both the Day 29 and Day 57 visits;
- Have not been compliant with the dosing regimen (i.e. subjects must apply 80 – 120% of the expected applications of study medication during participation in the study);
- Out of visit window at the Day 85 visit by  $\pm 7$  days;

Subjects that discontinue from the study due to an AE related to study treatment or documented lack of treatment effect will be included in the PP population. Prior to breaking the blind, other additional criteria may be added to the list to accommodate for unforeseen events that occurred during the conduct of the trial that result in noteworthy study protocol violations.

All efficacy analyses will be performed on the PP population with results considered as supportive.

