### **6.8.1 Primary Efficacy Analysis**

The proportion of subjects with IGA success defined as an IGA score of Clear (0) or Almost Clear (1) with at least a 2-grade improvement from Baseline at Day 85 will be analyzed using logistic regression with a term for treatment.

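### No ITT rule covers an IGA recorded after rescue or prohibited AD treatment, so clearance by another therapy counts by default as success for the assigned arm

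*Protocol*

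**What the plan says.** **Other treatment during the study.** Protocol 6.5 lists among prohibited treatments "Use of any topical agent, other than study drug, to treat AD", and also oral medication for AD. Protocol 6.6 then covers the subject who cannot go on without more treatment of the lesions, or who needs systemic treatment: "the appropriate treatment should be administered", the exacerbation is recorded as an AE, and the subject's "continuation on the study will be decided on a case-by-case basis". For infections needing antibiotics, Protocol 6.5 is explicit that "the subject can be treated and allowed to remain on the study". So the protocol expects some subjects to stay after otherwise prohibited treatment.

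**Primary analysis.** The endpoint in SAP 5.1.1 is an IGA of 0 or 1 "with at least a 2-grade improvement from Baseline at Day 85", with no condition on other treatment. The ITT set in SAP 6.4.2 is "All subjects in the randomized population who receive at least one application of study drug and have at least one post-Baseline efficacy assessment". SAP 6.8.1 says the endpoint "will be analyzed using logistic regression with a term for treatment".

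**Where interfering medication matters.** The only analysis rule on it is in SAP 6.4.5, where subjects who "Have taken any interfering concomitant medication" are excluded from the per-protocol set. The same section keeps in that set subjects who discontinue for a related AE or for documented lack of effect.

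**The concern.** A subject whose AD worsens, who is given another effective therapy, stays on study and is clear at Day 85 has not been cleared by the study product. Nothing in the plan separates that subject from one cleared by BTX 1204 or vehicle alone. If the arms differ in how often rescue is used, the primary difference reflects both the study drug and the rescue therapy.

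A Phase 2a primary estimate will be used to judge whether to continue development. A choice made after unblinding about how to treat these subjects would carry little weight.

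**Working it through.** **Step 1: follow one value through the rules.** Take a subject rescued after Day 29, kept on study, with an IGA of 1 at the scheduled Day 85 visit.

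- Endpoint (SAP 5.1.1): baseline 3, now 1, so the definition is met.
- Analysis set (SAP 6.4.2): included. SAP 6.1 makes ITT primary.
- Visit (SAP 6.1.3): the nominal Day 85 value is used.
- Missing data (SAP 6.1.5): LOCF fills missing values, and this one is present.
- Model (SAP 6.8.1): treatment term only, so the subject is a success for the assigned arm.
- GEE sensitivity analysis (SAP 6.10.1): uses data from every post-baseline visit, so the value stays.
- Tipping point (SAP 6.10.2): varies missing outcomes only, so the value stays.
- Changes to planned analyses (SAP 8): no rule on rescue.

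Withdrawal does not fully close the route. Protocol 4.3 asks for the Day 85 assessments at withdrawal. SAP 6.1.3 maps an early-termination value on study days 71 to 98 to Day 85. An earlier value can fill an empty earlier window and be carried forward by LOCF.

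**Step 2: per-protocol set.** A rescued subject who stays on study is excluded if the medication is classed as interfering. One who discontinues for documented lack of effect is kept, though SAP 6.1.5 uses available data only in this set. The rescued completer is therefore removed, not counted as a failure.

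**Step 3: size.** There is no plan figure to reproduce: SAP 7 sets 100 per arm on clinical considerations only. All rates below are assumptions.

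- Let p be the share of all subjects in an arm who succeed without rescue, r the share rescued, and q the share of rescued subjects scored as success.
- Rescued counted as failures: rate = p. Rescued counted as observed: rate = p + r × q.
- Difference as observed = (pA − pV) + q × (rA − rV), where A is active and V vehicle.
- Power (two-sided 0.05, n = 100 per arm, p̄ the mean of the two rates) = Φ{[Δ − 1.96√(2p̄(1−p̄)/n)] / √([pA(1−pA) + pV(1−pV)]/n)}, with the relevant rates put in.

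With pV = 15% and pA = 30%, rescue counted as failure gives 15.0 points and power 72%. With post-rescue values counted as observed:

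| Rescue V / A | q | Rate V | Rate A | Difference (points) | Power |
|---|---|---|---|---|---|
| 2% / 1% | 30% | 15.6% | 30.3% | 14.7 | 70% |
| 10% / 10% | 30% to 50% | 18% to 20% | 33% to 35% | 15.0 | 69% to 66% |
| 10% / 5% | 30% to 50% | 18% to 20% | 31.5% to 32.5% | 13.5 to 12.5 | 60% to 52% |
| 20% / 10% | 30% to 50% | 21% to 25% | 33% to 35% | 12.0 to 10.0 | 48% to 34% |
| 5% / 10% | 30% to 50% | 16.5% to 17.5% | 33% to 35% | 16.5 to 17.5 | 78% to 81% |
| 10% / 20% | 30% to 50% | 18% to 20% | 36% to 40% | 18.0 to 20.0 | 82% to 88% |

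The 10 to 20 point range holds when rescue lies in 5-20% and the arms differ at most twofold. At 5% against 20% with q = 50%, the shift is 0.50 × 15 = 7.5 points, giving 7.5 or 22.5.

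With no true difference (15% rescue-free success in both arms) and rescue of 5% on vehicle and 15% on active, the chance of nominal significance favouring active is 8% (q = 30%) to 14% (q = 50%), against 2.5% in that direction.

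**The case against.** **No sentence in the plan credits post-rescue clearance to the study arm.** True. A reader might infer that the SAP adopted this as a rule; it did not. It is what the written steps produce when nothing interrupts them. The defect is an unspecified rule with a definite default result.

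**The as-observed ITT analysis answers a legitimate question.** It does: the treatment-policy question, in which other therapy is part of the course of care. It would be too strong to say that neither the ITT nor the per-protocol analysis informs the comparison. But neither document names that estimand or gives a reason for it.

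**The bias must shrink the effect, since vehicle subjects will need more rescue.** This inference is tempting, but the documents give no rescue rates by arm. Step 3 shows dilution, no change or inflation depending on the split.

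**The per-protocol set drops every rescued subject.** It does not. SAP 6.4.5 keeps those who discontinue for documented lack of effect, and criteria can be added before the blind is broken.

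**The affected group may be very small.** This stands. Other AD treatment is prohibited and a rescued subject may be withdrawn, so the distortion mainly needs rescue, continuation and an IGA success together. At 1-2% rescue it is negligible.

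**Power is a weak yardstick here.** This also stands. The sample size has no power target and SAP 6.1.8 calls the tests exploratory. The shift in the estimated difference is the relevant measure.

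**Conclusion.** The concern holds as a gap with a default consequence. Followed exactly, the plan scores clearance after other AD treatment as success for the assigned arm in the ITT primary analysis, and both sensitivity analyses leave it in place. The per-protocol analysis does not fill the gap, because rescued subjects who stay on study are removed from it and not failed.

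The direction of bias is not fixed. Under the stated assumptions a 15-point difference reads as 10 to 20 points, does not move when rescue is equal, and hardly moves when rescue is rare. None of the rates comes from the documents. Because the trial is exploratory, what is at stake is how the primary estimate is read, not control of type I error. The change should be made, and made before unblinding.

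**What to change.** Add to SAP 6.8.1: in the ITT primary analysis, a subject is an IGA non-responder at every visit after first use of a prohibited topical or systemic treatment given for AD. Keep the as-observed (treatment-policy) analysis as a named sensitivity analysis.

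Identify first use by a flag set under blind from the concomitant-medication data. Protocol 6.4 already has all such medication recorded, and Listing 16.2.4.3.2 carries indication, route and dates. The SAP must define the flag itself, because SAP 6.3 says deviations will not be entered in the database. It should also state how partial start dates are handled, since SAP 6.6 treats ambiguous ones as falling before first application. Limiting the flag to treatment given for AD leaves out antibiotics for an infection.

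The cost is a few sentences, one derived flag and one extra sensitivity table. Success rates may read slightly lower, and the estimand becomes explicitly composite: success without other AD treatment. Even brief use of a prohibited AD treatment would count as failure, which is why the as-observed analysis should be shown beside it. Per-protocol membership and rescue care need no change.

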6.7. Subject Access to Study Agent at Study Closure

Subjects will not have access to the study drug after completion of their participation until the product is available commercially.

7. ASSESSMENT OF SAFETY

7.1. Specification of Safety Parameters

7.1.1. Definition of Adverse Events (AE)

An AE is defined as any untoward medical occurrence in a study subject which does not necessarily have to have a causal relationship with the study treatment. An AE can therefore be any unfavorable and unintended sign (including an abnormal laboratory finding), symptom, or disease temporally associated with the use of study drug treatment, whether or not considered related to the study drug.

Any events involving illnesses or injuries with onset during the study or any events involving exacerbations of pre-existing illnesses should be recorded. All clearly related signs and symptoms should be grouped together and recorded as a single diagnosis in the eCRF. A pre-existing condition will not be reported as an AE unless the condition worsens during the trial. The condition, however, must be reported in the Medical History section of the eCRF. Scheduled or planned diagnostic and therapeutic procedures such as surgery will not be reported as AEs.

7.1.2. Definition of Serious Adverse Events (SAE)

Each AE will be independently judged by the investigator in terms of seriousness. A serious AE (SAE) is defined as any untoward medical occurrence that:

- Results in death,
- Is life-threatening,

Note: The term “life-threatening” in the definition of “serious” refers to an event in which the subject was at risk of death at the time of the event; it does not refer to an event which hypothetically might have caused death if it were more severe.

- Requires inpatient hospitalization or prolongation of existing hospitalization,
- Results in permanent impairment of a body function or permanent damage to a body structure,
- Is a congenital anomaly/birth defect,
- Necessitates medical or surgical intervention to preclude any one of the outcomes listed in this definition.

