7.2.2. Severity of Event

Each sign or symptom reported will be graded on a 5-point severity scale (Grade 1, 2, 3, 4 and 5).

The following definitions for rating severity will be used:

Grade 1	Mild; asymptomatic or mild symptoms; clinical or diagnostic observations only; intervention not indicated.
Grade 2	Moderate; minimal, local or noninvasive intervention indicated; limiting age-appropriate instrumental activities of daily living.*
Grade 3	Severe or medically significant but not immediately life-threatening; Hospitalisation or prolongation of hospitalisation indicated; disabling; limiting self-care activities of daily living.** Note: An experience may be severe but may not be serious, (e.g., severe headache).
Grade 4	Life-threatening consequences; urgent intervention indicated.
Grade 5	Death related to AE.

Note: A semi-colon indicates 'or' within the description of the grade.

*Instrumental activities of daily living refer to preparing meals, shopping for groceries or clothes, using the telephone, managing money, etc.

**Self-care activities of daily living refer to bathing, dressing and undressing, feeding self, using the toilet, taking medications, and not bedridden.

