7.4.2. Serious Adverse Event Reporting

Each AE will be independently judged by the investigator in terms of seriousness. A SAE is defined in Section 7.1.2.

All SAEs will be reported to the sponsor via e-mail or phone call within 24 hours of becoming aware of the event, whether or not the serious events are deemed drug-related. All serious event reporting will adhere to 21 CFR 312.32 for Investigational New Drugs (IND) and to the Guidance for Industry and Investigators: Safety Reporting Requirements for INDs and Bioavailability/Bioequivalence, dated December 2012. The HREC/IRB will be notified of the Alert Reports.

All AEs will be followed until resolution or until the investigator determines that the subject's status has returned to normal or has stabilized.

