**Listing sorted by Subject, Start Date, End Date, and Adverse Event.**

**Programming Notes:** If an adverse event is indicated as serious the reason(s) for the event being serious will be listed under the R: Reason(s) for Serious column and separated by a comma. Possible reason(s) include: Fatal, Life-threatening event, Hospitalization or prolongation of hospitalization, Persistent or significant disability/incapacity, Congenital Anomaly or Birth Defect, Important Medical Event.

Listing 16.2.7.1.3: Serious Adverse Events  
 Treatment Group  
 (Page xx of yy)

S: Subject	A: Adverse Event	S: Start Date (Day) 	S: Severity	S: Is AE Serious?
A: Age/Sex	C: System Organ Class	E: End Date (Day) 	R: Relationship to Study Drug	R: Reason(s) for Serious
E: Evaluable	P: Preferred Term	A: Action Take with Study Treatment	O: Outcome	T: Medical Treatment Received?
S: xxxxxx	A: xxxxxxxxxxxxxxxx	S: xxxx-xx-xx (xx)	G: xxxx	S: xx
A: xxx xx	C: xxxxxxxxxxxxxxxx	E: xxxx-xx-xx (xx)	R: xxxxxxxxxxxx	R:
E: xxxxxxxxxxxx	P: xxxxxxxxxxxxxxxx	A: xxxx xxx xxxxxxxx	O: xxxxxxxxxxxx	T: xxx
S: xxxxxx	A: xxxxxxxxxxxxxxxx	S: xxxx-xx-xx (xx)	G: xxxx	S: xxx
A: xxx xx	C: xxxxxxxxxxxxxxxx	E: xxxx-xx-xx (xx)	R: xxxxxxxxxxxx	R: xxxxxx xxxxxxxx
E: xxxxxxxxxxxx	P: xxxxxxxxxxxxxxxx	A: xxxx xxx xxxxxxxx	O: xxxxxxxxxxxx	T: xxx
S: xxxxxx	A: xxxxxxxxxxxxxxxx	S: xxxx-xx-xx (xx)	G: xxxx	S: xxx
A: xxx xx	C: xxxxxxxxxxxxxxxx	E: xxxx-xx-xx (xx)	R: xxxxxxxxxxxx	R: xxxxxxxxxxx xxxxxxxx
E: xxxxxxxxxxxx	P: xxxxxxxxxxxxxxxx	A: xxxx xxx xxxxxxxx	O: xxxxxxxxxxxx	T: xxx

  Day = (date - date of first dose + 1) for dates on or after first dose. Otherwise, Day = (date - date of first dose).  
 Note: System Organ Class and Preferred Term map to MedDRA (Version xx.x).  
 SOURCE: USERNAME\SPONSOR\PROJECT\JOBNAME (DATE, TIME)

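### The SAE definition in Protocol 7.1.2, which triggers 24-hour reporting, does not match the seriousness reasons in the SAP listing note: two of six differ, chiefly on non-permanent disability

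*Protocol*

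**What the plan says.** Protocol 7.1.2 has the investigator judge each AE for seriousness against six criteria. The fourth is "Results in permanent impairment of a body function or permanent damage to a body structure". The sixth is "Necessitates medical or surgical intervention to preclude any one of the outcomes listed in this definition". The other four are death, threat to life, inpatient hospitalization or its prolongation, and congenital anomaly or birth defect.

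Protocol 7.4.2 sets the reporting duty: "All SAEs will be reported to the sponsor via e-mail or phone call within 24 hours of becoming aware of the event". It takes the definition from the earlier section: "A SAE is defined in Section 7.1.2". It also commits serious event reporting to 21 CFR 312.32, without reproducing what that rule says.

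The SAP contains no SAE definition of its own. The programming note under Listing 16.2.7.1.2 says what may appear in the column for the reason an event was serious: "Possible reason(s) include: Fatal, Life-threatening event, Hospitalization or prolongation of hospitalization, Persistent or significant disability/incapacity, Congenital Anomaly or Birth Defect, Important Medical Event". SAP 6.11.2 plans a summary of serious TEAEs by system organ class and preferred name, which is Table 14.3.1.3.

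**The concern.** The definition that sets the seriousness flag and the list from which the reasons are to be reported should be the same list. They are not. The SAP note has a reason for disability that is persistent or significant, while 7.1.2 asks for permanence. The SAP note has a reason for important medical events, while 7.1.2 reaches such events only through the need for intervention.

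The label and the timing are at stake. An investigator who follows 7.1.2 as written could properly answer no to seriousness for an event that the SAP's own list would count as serious. That event would then carry no 24-hour duty under the 7.1.2 definition and would not be counted among the serious TEAEs. Safety is part of the study's stated objective, so the serious-event table should rest on one definition that can be stated plainly.

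**Working it through.** No calculation applies. The check sets the two lists side by side and then follows the seriousness flag through to the tables.

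**Step 1. Compare the criteria.**

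| Protocol 7.1.2 | SAP note, Listing 16.2.7.1.2 | Match? |
|---|---|---|
| Death | Fatal | Yes |
| Life-threatening | Life-threatening | Yes |
| Inpatient hospitalization or prolongation | Hospitalization or prolongation | Yes |
| Permanent impairment of function, or permanent structural damage | Disability or incapacity, persistent or significant | No |
| Congenital anomaly or birth defect | Same | Yes |
| Intervention needed to prevent a listed outcome | Important medical event | Partial overlap only |

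Four reasons match and two do not (4 + 2 = 6).

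**Step 2. Find which list sets the flag.** Section 7.1.2 gives the judgement to the investigator. Section 7.4.2 points back to 7.1.2 and attaches the 24-hour duty to SAEs. Section 7.4.1 records seriousness on the AE eCRF as yes or no and does not name a reason among the recorded items. The serious TEAE table is built from events flagged as serious. On the text, 7.1.2 is therefore the operative definition.

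**Step 3. Run four types of event through 7.1.2.**

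- *Significant but reversible incapacity, no hospitalization, no threat to life, no intervention needed to avert a listed outcome.* It meets none of the six criteria, yet it fits the SAP disability reason. Severity grading does not change this. Grade 3 in 7.2.2 takes in disabling and medically significant events, but the same section says that a severe event may not be serious.
- *Important medical event that needs intervention to avert a listed outcome.* It is serious under the sixth criterion, so there is no gap.
- *Important medical event that needs no such intervention and meets no other criterion.* It is outside 7.1.2 and inside the SAP list.
- *Permanent structural damage that is not disabling.* It is serious under 7.1.2, but the SAP note has no direct reason for it.

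The first and third types are the gap in the protocol. The fourth is a smaller gap in the other direction, so neither list contains the other.

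**Step 4. See what still captures an event in the gap.** All AEs from consent through the Day 85 visit are recorded (7.3). The medical monitor reviews blinded safety data in real time (11.1.6), and 7.5 sets a monthly minimum for safety review. An event graded severe with onset on or after the first application appears in Table 14.3.1.5. What the event could lose is the 24-hour report and its place in Table 14.3.1.3.

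**The case against.** The strongest reply is that this is a difference between a protocol definition and a note to programmers, and that little turns on it.

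Several parts of that reply stand. The SAP text is a note on how to fill a listing column and does not define an SAE. The sixth criterion of 7.1.2 takes in important medical events that need intervention to prevent a listed outcome, and it also covers part of the disability gap, where intervention is needed to prevent permanent impairment. Other safeguards remain. All AEs are recorded with severity, the sponsor must be told at once of a withdrawal because of an AE (4.3), source data verification is complete (8), and severe, related and discontinuation-causing TEAEs each have their own table. The reference to 21 CFR 312.32 in 7.4.2 may also narrow the reporting gap. Its content is not in the documents, so the extent cannot be judged here.

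The reply does not remove the mismatch. Section 7.4.2 names 7.1.2 as the definition, and no 7.1.2 criterion reaches a significant, reversible disability on its own.

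A reader might infer three stronger things that the documents do not support:

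- *That sites will classify the same event differently.* Nothing shows that sites see or use SAP programming notes. The eCRF is not among the documents. If it carried the SAP reasons, it would prompt sites towards the broader list.
- *That the medical monitor depends on 24-hour reports to learn of such events.* Section 11.1.6 describes real-time review of blinded safety data.
- *That any important medical event can go unreported as serious.* Only those that need no intervention to avert a listed outcome, and meet no other criterion, are outside.

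**Conclusion.** The inconsistency is real and limited. Two of the six SAP reasons lack an equivalent in 7.1.2. The disability criterion is the clearer of the two. The important-medical-event gap is confined to events without qualifying intervention. The consequence is possible loss of the serious label, of the 24-hour report, and of the entry in Table 14.3.1.3. It does not mean that an event goes unrecorded or unreviewed.

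How often this would happen cannot be derived from the documents, and any assumed incidence would have no source. Sample size and efficacy analyses are unaffected.

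The conclusion rests on two assumptions: that investigators apply 7.1.2 as written, and that no eCRF instruction or other study document supplies a wider definition. It also leaves open what 21 CFR 312.32 would add.

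**What to change.** Reconcile Protocol 7.1.2, Protocol 7.4.2 and the SAP reasons to one list.

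1. In 7.1.2, keep the existing bullets on permanent impairment or damage and on intervention. Add the SAP's own two terms, for disability or incapacity and for important medical events. The permanent-damage bullet should not be replaced, because permanent damage that is not disabling would then lose its explicit criterion.
2. Leave 7.4.2 pointing to 7.1.2, so that the 24-hour duty follows the reconciled list.
3. In the SAP note to Listing 16.2.7.1.2, add a reason for permanent structural damage.
4. Check that the eCRF, which could not be seen here, agrees with the same list.

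The cost is a protocol wording amendment, which under 11.1.2 needs IRB/EC approval before it is implemented, and a small SAP edit. A few more events may be reported as serious. Events judged before the amendment would need a second look if Table 14.3.1.3 is to rest on a single definition.
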